9.3. Withdrawal from Study

Withdrawal from study (including all follow-up) will occur under the following circumstances:

1. Withdrawal of consent for follow-up observation by the subject
2. Lost to follow-up
3. Study termination by Pharmacyclics or study sponsor
4. Death

If a subject is lost to follow-up, every reasonable effort should be made by the study site personnel to contact the subject. The measures taken to follow up should be documented.

When a subject withdraws before completing the study, the following information should be documented in the source documents:

1. Reason for withdrawal
2. Whether the subject withdraws full consent (i.e. withdraws consent to treatment and all further contact) or partial consent (i.e. withdraws consent to treatment but agrees to participate in follow-up visits)

10. STATISTICAL METHODS AND ANALYSIS

10.1. Subject Information

All patients receiving at least one cycle of therapy and are evaluable for response will be assessable for the primary endpoint of progression free survival (evaluable population).

10.2. Endpoints

10.2.1. Primary Endpoint

The primary analytic objective of this Phase IB/II study is provide a preliminary assessment of the efficacy of this treatment combination, as measured by Progression-Free Survival (PFS).

10.2.2. Secondary Endpoints

Secondary analytic objectives are to provide preliminary assessments of the RECIST Response Rate, Overall Survival, and Safety of this treatment combination.

10.2.3. Other Secondary Endpoints

N/A

10.2.4. Exploratory Endpoints

N/A

10.3. Sample Size Determination

In the RECORD-1 trial, PFS at 6 months was approximately 40%. Assuming that the ibrutinib plus nivolumab combination will increase the PFS rate from 40 to 70% at the 6 month timepoint, a sample size of 25 patients will provide 90% power and one-sided level 0.034 to detect this difference, with a critical value of 15 or more patients out of 25 experiencing PFS at 6 months. To account for dropouts, a total of 30 patients will be accrued. Efficacy analysis will be performed on all patients enrolled in the study regardless of dose level assignment; i.e., patients from each of the completed dose levels will be pooled as described in the study schema.

10.4. Analysis Populations

10.4.1. Safety Population

The safety population will include all patients who receive at least one dose of either study drug. A baseline measurement and at least one laboratory, vital sign, or other safety-related measurement obtained after at least one dose of study medication may be required for inclusion in analyses of a specific safety parameter.

10.4.2. Efficacy populations

Evaluable population:

The evaluable population will be the basis for the primary analysis of efficacy (progression-free survival). This population will include all patients who complete at least one cycle of therapy at either of the two planned dose levels and are evaluable for the primary response (progression-

free survival). Secondary analyses may require instead that patients be evaluable for secondary efficacy analyses (RECIST response, overall survival.)

Per-protocol population:

A supportive analysis may be carried out using the per-protocol population, defined as a subset of the evaluable population that further excludes patients who experienced deviations from protocol that may affect primary or secondary outcomes.

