10.5. Statistical Methods

Primary endpoint: Progression-free survival (PFS) as the number of months from baseline to death or progression, defined in Appendix 4. The duration of PFS will be summarized descriptively using Kaplan-Meier survival plots and life tables. The number and proportion with PFS of 6 months or more will be reported, adjusting for censoring using the life-table approach. If the number with PFS at least six months is 15 or more out of 25 evaluable patients, this will constitute evidence supporting an improvement over historic PFS rates.

Secondary endpoints: RECIST response will be calculated as in Appendix 4, and will be summarized by the number and percentage of patients, accompanied by 2-sided exact 95% confidence intervals. Overall survival will be summarized descriptively by Kaplan-Meier curves and life table estimates, as for PFS. Number and type of adverse events will be summarized descriptively by system organ class affected and by grade of event, overall and by dose. Vital signs and laboratory test results will be summarized descriptively (mean, SD, range) overall and by dose.

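### The primary 6-month PFS test leaves out patients who do not get through cycle 1, and Section 10.4 defines no PFS analysis in all treated patients

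*Combined protocol and SAP*

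**What the plan says.** Section 10.5 of the combined protocol and SAP defines the primary endpoint as "Progression-free survival (PFS) as the number of months from baseline to death or progression". A death or progression in the first 28-day cycle is therefore a primary-endpoint event.

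Three places limit who is tested:

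- Section 10.1: "All patients receiving at least one cycle of therapy and are evaluable for response will be assessable for the primary endpoint of progression free survival".
- Section 10.4.2: "This population will include all patients who complete at least one cycle of therapy at either of the two planned dose levels". Patients must also be evaluable for PFS, a condition that is not defined further.
- Section 10.5, the decision rule: "If the number with PFS at least six months is 15 or more out of 25 evaluable patients", the result counts as evidence of improvement over historical rates.

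Sections 10.1 and 10.4.2 do not quite agree. The first asks that a cycle be received, the second that it be completed.

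The only other efficacy set in 10.4.2 is per-protocol, "defined as a subset of the evaluable population that further excludes patients who experienced deviations from protocol". The set of all patients given at least one dose appears in 10.4.1, for safety only.

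Section 10.3 adds: "Efficacy analysis will be performed on all patients enrolled in the study regardless of dose level assignment". Its own explanatory clause says that this means pooling the dose levels. The same section allows for loss: "To account for dropouts, a total of 30 patients will be accrued".

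**The concern.** Entry to the primary test depends on something that happens after baseline and is related to the outcome. A patient who dies on day 20 has had a PFS event but never enters the count. The same holds for a patient who stops within the first 28 days and fails before month 6. If those left out fail more often than the rest, the evaluable set looks better than the treated group, and 15 of 25 becomes easier to reach than the stated level suggests.

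The consequence is limited in two ways. The first scheduled on-treatment scan is at Cycle 3 Day 1, about 8 weeks in, so most early progressors would finish cycle 1 and be counted. The main loss is deaths and stops within cycle 1. Also, stopping for toxicity is not itself a PFS event; it matters only through what follows.

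The rule carries the trial's efficacy conclusion, and no analysis defined in 10.4 would show a reader how far it depends on the patients left out.

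**Working it through.** **Inputs.** From Section 10.3: null rate 0.40, target rate 0.70, 25 patients, success at 15 or more, one-sided level 0.034, power 90%, 30 accrued. The documents give no cycle-1 failure rate, so the shares below are assumptions.

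**Step 1: the plan's own figures (exact binomial).**
- P(X ≥ 15 | n=25, p=0.40) = 0.0344, matching the stated 0.034.
- P(X ≥ 15 | n=25, p=0.70) = 0.9022, matching the stated 90%.

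The design arithmetic is right for 25 evaluable patients.

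**Step 2: level read as a statement about all treated patients.** Suppose the true 6-month rate in all treated patients is 0.40, a share e is excluded, and a fraction f of those excluded fail by month 6. The rate in the patients kept is

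p = (0.40 − (1 − f)e) / (1 − e).

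At f = 0.60 this is 0.40(1 − e)/(1 − e) = 0.40 for any e, so the level does not change. Above 60% it rises; below 60% it falls. With 25 patients kept, P(X ≥ 15 | n=25, p) is:

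| Share excluded, e | f = 1.0 | f = 0.8 | f = 0.6 | f = 0.5 |
|---|---|---|---|---|
| 1% | 0.038 | 0.036 | 0.034 | 0.034 |
| 3.3% | 0.047 | 0.040 | 0.034 | 0.032 |
| 6.7% | 0.064 | 0.047 | 0.034 | 0.029 |
| 16.7% (5 of 30) | 0.159 | 0.080 | 0.034 | 0.021 |

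Example: e = 6.7%, f = 1 gives p = 0.40/0.9333 = 0.4286 and a level of 0.064.

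The rows are shares with 25 patients kept. Only the last is also a count out of 30, since 30 − 5 = 25. Excluding one or two of 30 would leave 29 or 28 evaluable, and the plan states no cut-off for those numbers.

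**Step 3: what omitted failures do to an observed result.** Tail probability at 0.40 when omitted failures are added back to the denominator:

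| Successes | n=25 | 26 | 27 | 28 | 29 | 30 |
|---|---|---|---|---|---|---|
| 15 | 0.034 | 0.052 | 0.074 | 0.103 | 0.136 | 0.175 |
| 16 | 0.013 | 0.022 | 0.034 | 0.050 | 0.071 | 0.097 |
| 17 | 0.004 | 0.008 | 0.013 | 0.022 | 0.033 | 0.048 |
| 18 | 0.001 | 0.003 | 0.005 | 0.008 | 0.014 | 0.021 |

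A result of 15/25 does not stay within 0.034 after a single omitted failure; 18/25 does so after five. At a true rate of 40%, 62% of declared successes are exactly 15/25; at 70%, 10% are. The exclusion matters most where a false positive is most likely.

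**Step 4: cut-offs for an all-treated analysis.** For 30 treated:
- 18 or more: level 0.021, power 0.916 at a true 70%.
- 17 or more: level 0.048, power 0.960.
- 15 or more: level 0.175.

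If 70% holds only in evaluable patients and k of 30 fail early, the success rate is 0.70(30 − k)/30. For k = 1 it is 0.677 and 18/30 has power 0.86; for k = 2 it is 0.653 and power is 0.79. For 17/30 the powers are 0.93 and 0.88.

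**The case against.** **Section 10.3 already refers to all enrolled patients.** It does, but its explanatory clause is about pooling doses, 10.4 sets up no such population, and nothing says how a patient who misses cycle 1 is counted. Read literally, it contradicts three other sections. Either way the text needs reconciling, and this is the most firmly documented part of the point.

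**The level is correct for the population the plan names.** This stands. The plan tests evaluable patients, and 0.034 is right for 25 of them. The inflation appears only when the result is read as describing all treated patients, and only if the 40% benchmark does so too. Section 10.3 does not give that trial's analysis set. If 40% came from a comparably restricted set, the mismatch would shrink or vanish.

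**Large exclusion shares have no support in the documents.** This also stands. The five extra patients are an allowance for dropouts, not a forecast of cycle-1 deaths, and the scan schedule favours a small share.

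**Early deaths are not hidden.** Section 11.4.2 requires deaths within 30 days of the last dose to be reported as serious adverse events, and the safety set includes everyone dosed. Readers would see them, but not in the PFS count.

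**The life table might deal with it.** Section 10.5 reports the 6-month proportion "adjusting for censoring using the life-table approach". That handles censoring among patients in the analysis; it cannot bring back those never admitted to it.

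**Conclusion.** The point holds as one about the analysis set. As written, the plan removes cycle-1 deaths, and cycle-1 stoppers who fail before month 6, from the primary test, and 10.4 offers no analysis that restores them. The wording in 10.3 leaves the intended set unclear.

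The size is unknown. If all excluded patients fail, the level for all treated patients is 0.038 with 1% excluded, 0.047 with 3.3% and 0.064 with 6.7%. The low end is the more plausible. These figures assume 25 evaluable patients and a 40% benchmark that applies to all treated patients. The clearest practical effect is at the boundary, where one omitted failure moves 15/25 to 15/26.

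A reader might infer that the stated 0.034 is wrong, or that the trial's true false-positive rate is near 0.159. The documents support neither. The 0.034 reproduces exactly, and 0.159 needs 5 of 30 patients to be excluded and all of them to fail. Nor must the exclusion favour the combination: below 60% failure among those excluded, the level falls. Inflation is the likelier direction only because early death is an obvious reason not to complete a cycle.

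For a preliminary single-arm study this should be fixed, but it does not invalidate the design.

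**What to change.** 1. Make Sections 10.1, 10.3, 10.4.2 and 10.5 name the same primary set, and settle whether a cycle must be received or completed.
2. Pre-specify a 6-month PFS analysis in all patients who receive at least one dose (the existing safety set), counting every death or progression before 6 months as a failure. Report it beside the evaluable analysis, or make it primary if the sponsor accepts the possible loss of power.
3. State its cut-off in advance for the number treated. For 30, choose 18 or more (level 0.021, power 0.916) or 17 or more (level 0.048, power 0.960), according to the level the sponsor accepts. For smaller numbers, the cut-offs that stay within 0.034 are 16/26 (power 0.875), 16/27 (0.920), 17/28 (0.897) and 17/29 (0.935). Do not carry over 15.

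**Cost.** Protocol wording, one added analysis and a slightly lower reported PFS rate. No extra patients are needed if 70% holds in all treated patients. If it holds only in evaluable patients, the all-treated analysis loses the power shown in step 4.

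**Separate but related.** Section 8.2.8 lists no disease assessment at end of treatment and Section 8.3 lists no imaging, while Appendix 1 marks CT/MRI in follow-up. These should be reconciled so that 6-month status is known for early stoppers.

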13. Currently active, clinically significant cardiovascular disease, such as uncontrolled arrhythmia or Class 3 or 4 congestive heart failure as defined by the New York Heart Association Functional Classification; or a history of myocardial infarction, unstable angina, or acute coronary syndrome within 6 months prior to enrollment.
14. Unable to swallow capsules or malabsorption syndrome, disease significantly affecting gastrointestinal function, or resection of the stomach or small bowel, symptomatic

inflammatory bowel disease or ulcerative colitis, or partial or complete bowel obstruction.

15. Lactating or pregnant.
16. Unwilling or unable to participate in all required study evaluations and procedures.
17. Unable to understand the purpose and risks of the study and to provide a signed and dated informed consent form (ICF) and authorization to use protected health information (in accordance with national and local subject privacy regulations).
18. Concomitant use of warfarin or other Vitamin K antagonists. Note: Subjects receiving antiplatelet agents in conjunction with ibrutinib should be observed closely for any signs of bleeding or bruising, and ibrutinib should be withheld in the event of any bleeding events. Supplements such as fish oil and vitamin E preparations should be avoided.
19. Requires treatment with a strong cytochrome P450 (CYP) 3A4/5 inhibitor. (see Appendix 3)
20. QT prolongation and/or familiar history of QT prolongation and uncontrolled cardiac arrhythmias that in the opinion of the investigator would interfere with the patient's safety or compliance on trial.
21. Currently active, clinically significant hepatic impairment Child-Pugh class B or C according to the Child Pugh classification (Appendix 10).

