5.3.1.5. Dose Modification for Hepatic Impaired Subjects

Ibrutinib is metabolized in the liver and therefore subjects with clinically significant chronic hepatic impairment at the time of screening (Child- Pugh class B or C) are excluded from study participation. For subjects with existing chronic mild hepatic impairment (Child-Pugh class A) at enrollment, the starting dose has to be adjusted to a level of 280 mg daily (two capsules). For subjects who develop mild liver impairment while on study (Child-Pugh class A), the recommended dose reduction for ibrutinib is to a level of 280 mg daily (two capsules) unless lower doses had already been implemented. For subjects who develop moderate liver impairment while on study (Child-Pugh class B), the recommended dose reduction is to a level of 140 mg daily (one capsule). Subjects who develop severe hepatic impairment (Child-Pugh class C) must hold study drug until resolved to moderate impairment (Child-Pugh class B) or better. Monitor subjects for signs of toxicity and follow dose modification guidance as needed (Refer to Appendix 10 and Section 5.3.1.4).

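### Sections 10.1, 10.3 and 10.4.2 word the primary efficacy set inconsistently, leave unclear whether required 280 mg starters belong to it, and give a success cut-off only for exactly 25 evaluable patients

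*Combined protocol and SAP*

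**What the plan says.** Three places in section 10 describe who enters the efficacy analysis.

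- **10.1** counts as assessable for PFS, under the label of evaluable population: "All patients receiving at least one cycle of therapy and are evaluable for response". It sets no dose condition.
- **10.3** says: "Efficacy analysis will be performed on all patients enrolled in the study regardless of dose level assignment". It then explains this by adding that "patients from each of the completed dose levels will be pooled as described in the study schema".
- **10.4.2** says: "The evaluable population will be the basis for the primary analysis of efficacy". Its entry rule is: "This population will include all patients who complete at least one cycle of therapy at either of the two planned dose levels", together with being evaluable for PFS.

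The table in 5.2.1 has two ibrutinib levels: Level 0 at 560 mg and Level -1 at 420 mg. On liver function, 4.2 excludes "Currently active, clinically significant hepatic impairment Child-Pugh class B or C", so class A patients can enrol. Section 5.3.1.5 then directs that for patients with "existing chronic mild hepatic impairment (Child-Pugh class A) at enrollment, the starting dose has to be adjusted to a level of 280 mg" daily.

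The decision rule in 10.5 is a count: "If the number with PFS at least six months is 15 or more out of 25 evaluable patients", the result supports an improvement over historical rates. Section 10.3 gives the same cut-off, with 30 patients accrued to allow for dropouts.

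**The concern.** The trial has one arm and is judged on one count, so membership of the denominator should follow from a single definition fixed before any data are seen. Two analysts working from this text could in good faith build different primary sets. One could leave out a 280 mg starter because that patient never took either listed dose. The other could keep the same patient under 10.1, or under 10.4.2 read as cohort assignment. On the first reading, a patient treated exactly as the protocol directs leaves the primary analysis because of hepatic function.

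A second gap makes the size of the denominator matter more. The accrual target exceeds the evaluable target by five, so the evaluable number may well not be 25, and the plan gives no cut-off for any other number.

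**Working it through.** **1. The definitions side by side.**

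| | 10.1 | 10.3 | 10.4.2 |
|---|---|---|---|
| Exposure | one cycle received | enrolled | one cycle completed |
| Evaluability | for response | none stated | for PFS |
| Dose condition | none | none (levels pooled) | one of two planned levels |
| 280 mg starter, full cycle, evaluable | in | in | out if dose received; in if assigned cohort |
| Less than one cycle | out | in, if taken literally | out |

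**2. Is 280 mg a planned level?** The evidence points both ways. Against: 5.2.1 lists two levels, 10.4.2 counts two, and the synopsis gives a range of 420 to 560 mg. For: the schema footnote in 3.1.1 mentions a Level -2, to which 5.2.1 assigns no dose. Section 3.2.2 describes the dose as two to four 140 mg capsules, and 2 × 140 = 280 mg. Table 1 in 5.3.1.4 also uses the term dose level for a step down to 280 mg.

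**3. Reproducing the design.** Inputs from 10.3: null rate 0.40, alternative 0.70, N = 25, cut-off c = 15. With X binomial(N, p),

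P(X ≥ c) = Σ from k = c to N of C(N,k) p^k (1 − p)^(N − k).

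At N = 25 and c = 15 this is 0.0344 at p = 0.40 and 0.9022 at p = 0.70. The stated 0.034 and 90% are correct. Accrual of 30 implies a loss of 5/30 = 16.7%.

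**4. Other evaluable numbers.** The left pair of results keeps the cut-off at 15. The right side uses the smallest cut-off whose alpha does not exceed the design's 0.0344.

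| N | alpha, c = 15 | power, c = 15 | cut-off holding alpha | alpha | power |
|---|---|---|---|---|---|
| 22 | – | – | 14 | 0.0215 | 0.8135 |
| 23 | 0.0128 | 0.7709 | 15 | 0.0128 | 0.7709 |
| 24 | 0.0217 | 0.8472 | 15 | 0.0217 | 0.8472 |
| 25 | 0.0344 | 0.9022 | 15 | 0.0344 | 0.9022 |
| 26 | 0.0518 | 0.9397 | 16 | 0.0217 | 0.8747 |
| 27 | 0.0743 | 0.9641 | 16 | 0.0337 | 0.9202 |
| 28 | 0.1025 | 0.9792 | 17 | 0.0215 | 0.8972 |
| 29 | 0.1362 | 0.9883 | 17 | 0.0329 | 0.9348 |
| 30 | 0.1754 | 0.9936 | 18 | 0.0212 | 0.9155 |

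One patient either way matters. From 25 to 24, power falls from 0.902 to 0.847. From 25 to 26 with 15 kept, alpha rises from 0.034 to 0.052.

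The c = 15 figures assume that every patient counted has the 40% null chance. If, at N = 30, the five extra patients are all certain failures, alpha stays at 0.034. The range for N = 30 is therefore 0.034 to 0.175.

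**5. Patients with less than one cycle.** As an illustration, suppose the true rate is 40% among all 30 and those who do not complete a cycle are all failures. Removing a fraction e raises the null rate in the evaluable set to 0.40/(1 − e). For one patient this is 0.40/(29/30) = 41.4%; for five, 0.40/(25/30) = 48.0%. The 15-of-25 rule then has a type I error of 0.047 and 0.159 respectively. The documents do not say how many such patients to expect.

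**The case against.** The strongest reply is that the governing set is already named. Section 10.4.2 identifies the evaluable population as primary, 10.1 uses the same label, and 10.5 ties the rule to evaluable patients. The sentence in 10.3 explains itself as a pooling statement. Within section 10, moreover, dose level most naturally means cohort: 10.3 speaks of assignment and of completed levels. On that reading the phrase in 10.4.2 only says that both cohorts are pooled, and a 280 mg starter stays in.

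Most of this stands. A reader might infer that the plan has three competing primary populations, or that it definitely excludes Child-Pugh A patients. The documents support neither. What remains is that 10.4.2 attaches the phrase to the therapy completed, not to assignment, and no text says how a 280 mg starter is classified.

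A reader might also infer that the trial runs at a type I error of 0.175. It does not: both statements of the rule tie 15 to 25, and no section applies 15 to 30 patients. That figure shows what would follow if the only stated cut-off were reused. It comes from the gap between 25 and 30, not from the 280 mg starters. The missing cut-offs would need attention even if no such patient enrolled.

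**Conclusion.** The wording is inconsistent and should be settled before analysis, but the point is minor. Whether 10.4.2 drops anyone depends on an undefined phrase. The number of patients exposed to that ambiguity is unknown and probably small.

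The missing cut-offs carry the larger numerical risk: with 15 reused, alpha would be 0.052 at 26 evaluable patients and up to 0.175 at 30, under the null-rate assumption given above. The design as stated for 25 patients is sound. Confidence is medium, because the schema to which 10.3 refers survives only as footnotes in the text available and might clarify the intended levels.

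**What to change.** 1. In 10.4.2, replace the dose condition with: *at any ibrutinib dose permitted by this protocol (assigned levels pooled)*.
2. Have 10.1 and the last sentence of 10.3 refer to the population in 10.4.2, so that 10.3 is purely a pooling statement. Report an all-treated analysis as a sensitivity analysis, because the evaluable set leaves out patients who progress or die before completing one cycle.
3. Beside the 15-of-25 rule, state the cut-off for the evaluable number actually obtained: 14 for N = 22; 15 for N = 23 to 25; 16 for N = 26 or 27; 17 for N = 28 or 29; 18 for N = 30. Each keeps one-sided alpha at or below 0.034. The cut-off of 18 of 30 is the same 60% as 15 of 25.

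The cost is protocol wording and one extra analysis, with no added patients or procedures. There are two downsides. Power falls below the stated 90% at N = 22 (0.814), 23 (0.771), 24 (0.847), 26 (0.875) and 28 (0.897). A few patients on 280 mg or less may slightly dilute the effect seen at full dose.
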